The primary outcome for hypothesis 1A is the proportion of prescribed doses taken according to the electronic monitor. Participants in both arms will receive the electronic monitor or "smart bottle," which wirelessly transmits the date and time of opening of the smart bottle to the study team. From these medication events, the proportion of prescribed doses will be derived, defined as the ratio of the number of times the smart bottle was opened to the required number of doses prescribed according to the medical record over the period of time that the bottle is in use. For example, if a participant is advised to take his or her glaucoma drop twice a day for the 180 days that the bottle is in use and the smart bottle reveals 135 openings over the same time period, the proportion of prescribed doses taken is 37.5%.

Specific Aim 2. Evaluate the impact of the intervention on intensification of glaucoma therapy among Veterans at 12-months post randomization.

Hypothesis 2: The proportion of Veterans in the intervention arm that are prescribed more intensive glaucoma therapy, defined as addition of adjuvant glaucoma medication or recommendation for laser or glaucoma surgery will be less than the proportion of Veterans in the control arm who are prescribed more intensive glaucoma therapy in the 12 months following the intervention.

Baseline data collection will include cataloging the current glaucoma medication regimen prescribed to the participant. Chart abstractions will be performed at approximately 12 months following the randomization and intensification of glaucoma therapy will be defined as either 1) the addition of another glaucoma medication to the baseline regimen, 2) recommendation for glaucoma laser treatment, or 3) recommendation for glaucoma surgery in the 12 months following randomization. We will collect these data at approximately 12 months because the Metrics study suggested that 55% of participants in the control arm will have intensification of therapy within one year.

Specific Aim 3. Evaluate the incremental cost-effectiveness and budget and workflow impacts of the intervention compared to usual care.

Hypothesis 3: The intervention will be cost-effectiveness for the following ratios: 1) cost per percentage improvement in medication adherence; 2) cost per blindness averted; and 3) cost per quality-adjusted-life years saved.

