A direct measurement approach will be used to estimate per-patient intervention and control arm costs. Glaucoma-related health care utilization costs will be derived from VA administrative datasets. The cost estimates will be combined with observed improvement in medication adherence and reduction in escalation in therapy to estimate the first two incremental cost effectiveness ratios. Simulation using Markov modeling will be used to estimate the incremental cost per blindness averted and quality-adjusted life years (QALYs) gained. Cost estimates and labor time data collected will be combined with glaucoma prevalence rates among Veterans to estimate overall budget and workload impacts to the VA healthcare system.

Risk/Benefit Assessment

The intervention is educational in nature and does not impose physical risks to participants. The primary risks to participants are loss of time and confidentiality. Participants' time was considered as an important factor in designing an intervention which is efficient yet hopefully effective. Actions taken to mitigate the risk of loss of confidentiality are addressed in the sections "Privacy and Confidentiality" and "Information Security." If, in the course of the study, any information becomes available that might influence the course of clinical care of the participant, this information will be communicated directly to the treating provider. The study offers no definitive benefit to participants but the knowledge gained may lead to improvements in the management of glaucoma for future patients.

Selection of Subjects

We will screen individuals until we meet the desired sample size of randomizing 200 Veterans and enroll up to 200 of their companions (family or friend) if a companion is available. Enrollment of a companion will not be required for otherwise eligible Veterans to be included in the study.

Inclusion criteria for patients at datapull:

- 1) Diagnosis of open angle glaucoma [primary open angle glaucoma, pigment dispersion glaucoma, pseudoexfoliation glaucoma, combined mechanism glaucoma, low tension glaucoma] recorded in the medical record,
- 2) Prescribed glaucoma eye drops,
- 3) Visual field performed within the last 9 months. As visual field testing is standard care glaucoma and we wish to establish baseline glaucoma severity, we will require that subjects have a visual field test documented in the chart within 18months of enrollment.

Exclusion criteria for patients:

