The primary outcome measure is each patient’s proportion of prescribed doses taken in the 6 months after the intervention according to the electronic monitor. We will use general linear regression models to test for a between-group difference in mean proportion of prescribed doses over 6 months. This regression model can be written as: $Y_i = \beta_0 + INT_i * \beta_1 + FREQ_i * \beta_2 + COM_i * \beta_3$, where Y_i represents the proportion of prescribed doses that patient i has taken through the 6-month follow-up. In this model, INT_i is the intervention group indicator; therefore, β_1 represents the mean difference in proportion of prescribed doses in the INT group as compared to the control group. We will formally evaluate the intervention effect by testing that β_1 differs from zero and report the mean difference and corresponding 95% confidence interval. A mean difference significantly greater than 0 provides evidence that INT group patients have a greater mean proportion of prescribed doses taken. The model will also include stratification

variables (frequency of glaucoma medication dosing (once vs more than once daily, FREQ)), companion (COM)) as recommended in the CPMP guidelines.⁶⁶

In addition to the preceding model, mean adherence will also be separated into six 30-day intervals and incorporated into a longitudinal model. This will allow us to understand trends of adherence over the course of the 6-month follow up period (e.g. initial improvements following the intervention followed by stability or decline). Non-linearity of these changes over time can be evaluated and contrasted between groups using SAS PROC MIXED. The richness of this adherence data will also enable us to explore particular patterns of nonadherence often associated with clinical progression of disease. For example, in exploratory analyses, we will examine whether intensification of therapy may be associated with running out of drops before the next available refill and missing the last week of dosing each month versus rationing drops such that drops are used only every 2-3 days.

Specific Aim 2: Evaluate the impact of the intervention on intensification of glaucoma therapy among Veterans at 12-month follow-up.

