Resource utilization. Expenditures are impacted not only by the cost of the intervention itself but also on other ophthalmology goods and services utilized. Therefore, we will collect glaucoma medication data from the VA Decision Support System Pharmacy extract. Using eye clinic stop codes and glaucoma diagnosis codes, we will collect outpatient costs incurred during the study period from DSS outpatient extracts.

Patient costs. Attendance of the one-on-one sessions will require the patients and/or companion to incur travel cost and may require that he/she miss work in order to attend the session. We will account for these indirect costs by asking the patients and companions to self-report how far they traveled round trip to attend the one-on-one session and whether they or their companion had to take time off from work to attend the session, and if so, how much time they took off. We will estimate travel cost by self-report and multiply the number of miles traveled by the deduction allowed by the Internal Revenue Service for medical-related travel. We will multiply time missed from work by an average hourly wage rate. The indirect costs reported in each arm will be aggregated and then divided by the respective group samples to estimate per-patient indirect cost.

Cost-Effectiveness. The 3 cost-effectiveness ratios that we will measure are: 1) cost per percentage improvement in medication adherence; 2) cost per blindness averted; and 3) cost per QALYs saved. We will consider the intervention to be cost-effective if the incremental cost-effectiveness ratio is \leq \$100,000 per QALY saved or \$150,000 per QALY saved, as recently recommended.⁶⁷ The estimation of these ratios are provided in the Data Analysis section below.

Data Analysis for Cost. The analysis will begin with standard descriptive statistics of the cost and effectiveness variables. We will then conduct bivariate analyses to assess statistical significance of group mean differences. If the main outcome is significantly different between the two groups, the first incremental cost-effectiveness ratio will be based on cost and improvement in medication adherence during the study period. However, incremental cost per blindness averted and QALYs saved will require simulating costs and outcomes among a larger hypothetical population and a time horizon beyond the study period. We will estimate

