these ratios by replicating the Markov model developed by the Centre for Eye Research Australia.⁶⁸ We will use 2nd order Monte Carlo simulation to incorporate probabilistic sensitivity analysis into the base-case estimates and to estimate confidence intervals of the incremental cost-effectiveness ratios. We will also conduct extensive parameter and model sensitivity analyses to assess the robustness of the base-case results. If the main outcome is not statistically significant between the two groups, then the economic analysis will focus on differences in intervention costs and health care costs between the two groups during the study period.

Budget and Workflow Impact. For planning purposes it will be helpful for VA administrators to know what impacts implementing this adherence intervention will have on budget and workflow. We will use US glaucoma prevalence information available in the literature⁶⁹ to extrapolate the number of Veterans that are likely to be affected by glaucoma annually. We will multiply this target patient population by the intervention and health care resource utilization costs observed first by the treatment arm patients and then by the control arm patients. The difference between these 2 estimates will be the incremental budget impact of the intervention. Similarly, we will multiply this target patient population by the amount of per-patient time required to conduct the intervention in the treatment and control arms and the incremental time will be the workflow impact. We will convert the incremental workflow impact to full-time equivalents (FTEs).

1. Kingman S. Glaucoma is second leading cause of blindness globally. *Bulletin of the World Health Organization* 2004;82:887-8.

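### Aim 3 makes the adherence cost-effectiveness ratio, and by implication the other two, depend on a significant Aim 1, so a non-significant result leaves Hypothesis 3 without a committed answer

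*Combined protocol and SAP*

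**What the plan says.** Under Outcomes, Specific Aim 3, the hypothesis is stated without condition: "Hypothesis 3: The intervention will be cost-effectiveness for the following ratios", followed by cost per percentage gain in adherence, per blindness averted and per QALY. The paragraph after it is also unconditional: "The cost estimates will be combined with observed improvement in medication adherence and reduction in escalation in therapy to estimate the first two" ratios, and "Simulation using Markov modeling will be used to estimate the incremental cost per blindness averted and quality-adjusted life years (QALYs) gained".

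The analysis section for Aim 3 adds the condition. Under Data Analysis for Cost: "If the main outcome is significantly different between the two groups, the first incremental cost-effectiveness ratio will be based on cost" and adherence improvement in the study period. The blindness and QALY ratios come next, with the remark that they need a larger simulated population and a longer horizon. The paragraph closes with the fallback: "If the main outcome is not statistically significant between the two groups, then the economic analysis will focus on differences in intervention costs", plus health care costs, within the study period.

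Two other statements matter. Under Cost-Effectiveness, "We will consider the intervention to be cost-effective if the incremental cost-effectiveness ratio is" at or below 100,000 or 150,000 dollars per QALY; no threshold is given for the other two ratios. Under Data Analysis for Cost, "We will use 2nd order Monte Carlo simulation to incorporate probabilistic sensitivity analysis into the base-case estimates", and the same simulation is to supply confidence intervals for the ratios.

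**The concern.** A significance test on adherence decides whether the economic question is pursued. A non-significant difference is not evidence of no difference, and a cost-effectiveness analysis is meant to combine an uncertain effect with an uncertain cost. The tool for that is already in the plan, yet the gate would set it aside when the effect is least certain.

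At stake is whether Hypothesis 3 gets an answer. Cost-effectiveness is judged only on the QALY ratio, so if that ratio is not produced the plan's own criterion cannot be applied. The outcome description and the analysis section also leave the reader unsure whether the ratios will exist after a non-significant Aim 1. That choice could then be made after the results are known.

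**Working it through.** **1. The text, ratio by ratio.**

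- *Adherence ratio.* Unconditional under Outcomes; explicitly conditional on significance under Data Analysis for Cost.
- *Blindness and QALY ratios.* Unconditional under Outcomes. Under Data Analysis for Cost they stand between the two branches with no condition of their own. The fallback is confined to the study period, and these ratios are said to need a longer horizon, so the fallback does not cover them. The condition is therefore implied, not stated.
- *Decision criterion.* Per QALY only.

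**2. What is reported whichever branch applies.** The Aim 1 model will "report the mean difference and corresponding 95% confidence interval". Descriptive and bivariate results for cost and effectiveness come before the gate. Budget and Workflow Impact carries no condition. None of these applies the QALY criterion.

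**3. How often the gate could close (illustration).** The plan has no figure to reproduce: it gives no SD, target difference, power or dropout for Aim 1.

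Inputs from the plan: 200 Veterans (Selection of Subjects) and 1:1 allocation (Randomization and Stratification), so n = 100 per arm. The test is two-sided at 5%, which is implied by testing that the coefficient differs from zero and by the 95% interval. The model has four coefficients, so there are 2n − 4 = 196 degrees of freedom.

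Assumptions: true standardised effects d of 0.2 to 0.5; 80 per arm with usable data as a variant; SDs of 20, 25 and 30 percentage points. The gate is taken to be the adjusted Aim 1 test. The plan does not say so, and the phrase for the main outcome directly follows a sentence on bivariate analyses.

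Smallest observed gain that opens the gate, in SD units: t(0.975, 2n − 4) × √(2/n).

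- n = 100: 1.972 × 0.1414 = 0.279 SD. This is 5.6, 7.0 or 8.4 points at the three assumed SDs.
- n = 80: 1.975 × 0.1581 = 0.312 SD.

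Chance that the gate closes (normal approximation): Φ(1.96 − d√(n/2)) − Φ(−1.96 − d√(n/2)).

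| True d | d√(n/2), n = 100 | Gate closed, n = 100 | d√(n/2), n = 80 | Gate closed, n = 80 |
|---|---|---|---|---|
| 0.2 | 1.414 | 71% | 1.265 | 76% |
| 0.3 | 2.121 | 44% | 1.897 | 52% |
| 0.4 | 2.828 | 19% | 2.530 | 28% |
| 0.5 | 3.536 | 6% | 3.162 | 11% |

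A simulation of 200,000 trials using the t test on 196 degrees of freedom gave 71%, 44%, 20% and 6% for n = 100.

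**4. Non-significant is not zero.** With 100 per arm, an observed gain of 0.25 SD has a 95% interval of 0.25 ± 1.96 × 0.1414, or −0.03 to 0.53 SD. The gate would be closed, yet most of that interval lies above zero.

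**5. Which ratios come first, and over what horizon.** The Outcomes text builds the first two ratios from adherence and therapy escalation. The Hypothesis 3 and Cost-Effectiveness lists put adherence first and blindness second, with no escalation ratio. The Aim 3 analysis text gives the first two ratios a 6-month horizon and gives blindness averted a lifetime horizon. Blindness, as second in the list, thus has two horizons, and escalation, a 12-month outcome under Aim 2, would be matched to 6 months.

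**The case against.** The best defence is that the plan sets a rule in advance with a stated fallback, and that only one ratio in three is expressly conditional. The fallback names a focus and does not exclude other analyses. The Outcomes paragraph is an outline, and Cost-Effectiveness refers to the later analysis text for how the ratios are estimated, so the detail may be read as governing. A ratio whose denominator is near zero is also hard to interpret.

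Much of this stands. A reader might infer that the plan forbids the blindness and QALY ratios after a non-significant Aim 1, or that Aim 3 would then yield nothing. The documents support neither: no condition is attached to those two ratios, and several results are reported regardless. What remains is the absence of a commitment. A focus on study-period costs does not promise a lifetime QALY ratio, and instability near zero effect calls for a different display, not for omission.

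A reader might also argue that ratios computed only after significance rest on overstated effects, and that removing the gate cures this. That does not support the change. In a trial with a significant Aim 1 the estimate and the ratio are the same with or without the gate; removing it adds results only where Aim 1 is not significant.

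Finally, the documents do not show how adherence enters the Markov model to be replicated, so carrying the adherence effect through it needs a specification the plan does not yet contain.

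**Conclusion.** The point holds as a gap in commitment. Following the analysis section after a non-significant Aim 1 leaves Hypothesis 3 with no assured answer on the plan's own per-QALY criterion, while the outcome description promises the ratios without condition. Aims 1 and 2 are unaffected.

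The size cannot be fixed from the documents. Over the assumed effects, closure ranges from 6% to 71% with 100 per arm, and from 11% to 76% with 80. These figures show that the gate could matter in a trial of this size. They are not probabilities of cost-effectiveness and not an estimate of this trial's power. They rest on the adjusted Aim 1 test being the gate and on a two-sided 5% level. The textual finding does not depend on them. The change is worth making but is not critical to the trial.

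**What to change.** Delete the significance condition from both branches of Data Analysis for Cost and state that the three planned ratios will be estimated whatever the Aim 1 p-value. Carry the uncertainty of the estimated adherence effect (the intervention coefficient and its standard error) through the second-order Monte Carlo simulation, and specify how adherence enters the Markov model. Report the probability of cost-effectiveness at each of the two QALY thresholds. Where the effect is near or below zero, show incremental cost and incremental effect jointly, because the ratio alone cannot then be interpreted.

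In the same revision, reconcile the Outcomes text, Hypothesis 3, the Aim 3 horizon statement and the Cost-Effectiveness list into one list of ratios with one horizon each. Either drop the escalation wording or match its costs to the 12-month outcome.

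The cost is mostly wording, plus specifying and running the Markov model when Aim 1 is not significant. How much modelling that takes cannot be judged from the documents, and the resulting intervals may be wide or include zero effect.

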Recruitment and Enrollment Process: We will use a recruitment strategy that was very efficient in our pilot studies. Potential participants will be identified by a data pull of Veterans with upcoming appointments at the DVAMC meeting inclusion/exclusion criteria. The medical records of potential participants identified by the data pull will be reviewed in detail to confirm eligibility based on the remaining inclusion/exclusion criteria. Potential participants confirmed to be eligible will be mailed a letter providing study information and a phone number to call to opt out of further contact regarding the study. Veterans who were mailed letters and did not opt out will be called by the study coordinator to discuss potential participation. If the Veteran is interested, screening questions will be asked to identify potential participants most likely to be poorly adherent to their prescribed glaucoma medication regimen. Veterans who screen positive for poor adherence and are interested in participation will be scheduled for an

appointment along with a companion if a companion is involved in his or her glaucoma management. Written informed consent and HIPAA authorization from the Veteran will be obtained at that time.

Recruitment Targets and Feasibility: We plan to randomize 200 Veterans (and enroll up to 200 companions if appropriate) over 24 months. Our pilot study identified 1533 Veterans meeting preliminary inclusion/exclusion criteria. In our pilot study, we used the proposed recruitment strategy and enrolled 31 Veterans over 3 months. In the proposed study, we will recruit 4-5 days/week, which greatly expands our ability to enroll and comfortably achieve our recruitment goal.

Consent Process

Potential participants who are eligible and express interest in the study after the screener phone call will meet in person with a member of the research team in a private room in the Durham VAMC or Hillandale clinic. The study will be described in detail and all questions answered. If the patient chooses to participate they will sign and date the informed consent and HIPAA forms. The signed informed consent and HIPAA documents safeguarded under lock and key at locations managed by the Durham VA Medical Center HSR&D: [name]. While we will go through a consent process for companions, we were granted a Waiver of Informed Consent Documentation and a Waiver of HIPAA Authorization for the companion.

Study Interventions

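### Budget and workflow impact are scaled to all Veterans with glaucoma, a larger group than the drop-using, screen-positive Veterans studied; the headcount is too large, but the direction of error in the net figures is open

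*Combined protocol and SAP*

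**What the plan says.** The extrapolation is set out under Data Analysis and Statistical Considerations, Specific Aim 3, Budget and Workflow Impact. Published US prevalence is used "to extrapolate the number of Veterans that are likely to be affected by glaucoma annually". The plan then says: "We will multiply this target patient population by the intervention and health care resource utilization costs observed first by the treatment arm patients", and next by those of the control arm. The difference is the budget impact. The same headcount times per-patient delivery time in each arm, again differenced, is the workflow impact, which is converted to FTEs. The Aim 3 text under Outcomes describes the same scaling: cost and labor data will be "combined with glaucoma prevalence rates among Veterans to estimate overall budget and workload impacts to the VA healthcare system".

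The trial population is narrower. Selection of Subjects requires "Diagnosis of open angle glaucoma" of listed types and "Prescribed glaucoma eye drops". A Veteran who reports both the highest level of confidence and no forgotten doses in the past four weeks is excluded at the screener. Under Recruitment and Enrollment Process, "screening questions will be asked to identify potential participants most likely to be poorly adherent to their prescribed glaucoma medication regimen", and only those who screen positive go on to enrolment.

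**The concern.** The plan calls every Veteran with glaucoma its target population, but the costs and times it multiplies come from a selected subgroup. Drop-technique coaching, a smart bottle and missed-dose reminders have no use for a Veteran who is not on drops, and Background and Significance names laser and surgery as other treatments. The utilisation difference was also measured only in Veterans who screened positive. Carrying it to adherent or untreated Veterans assumes they have the same room to improve. The screening call that identifies the target group is not among the listed cost or time inputs.

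The plan says these figures are for VA administrators to use in planning. As written, they describe a programme for people for whom it was neither designed nor tested. The primary outcome, Aim 2 and the three cost-effectiveness ratios are not affected.

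**Working it through.** The documents give no prevalence, unit cost, budget or FTE figure, so there is no stated result to reproduce. The check uses the plan's own formulas.

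**Formulas.** Budget = N × (C_int − C_ctl). Workflow = N × (T_int − T_ctl). The plan sets N to all Veterans with glaucoma. For the population studied, N becomes N × d × s, where d is the share on drops and s is the share of those who screen positive. An open-angle share would reduce it further, unless the prevalence source is already limited to open-angle disease. That source is not in the reference list supplied, so this cannot be checked.

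**Headcount ratio, 1/(d × s).** Neither share is in the documents; all values are assumptions.

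| d | s | 1/(d × s) |
|---|---|---|
| 0.9 | 0.9 | 1.23 |
| 0.7 | 0.5 | 2.86 |
| 0.5 | 0.3 | 6.67 |

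**Budget, per 1,000 Veterans with glaucoma, at d = 0.7 and s = 0.5.** The eligible number is 1,000 × 0.7 × 0.5 = 350. The per-patient differences are assumed.

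- +$100: 1,000 × 100 = $100,000 as planned, against 350 × 100 = $35,000. A cost is overstated.
- −$200: −$200,000 as planned, against −$70,000. A saving is overstated, so the net cost is understated.

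The sign is not fixed in advance, because Aim 3 expects less escalation of therapy in the intervention arm.

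**Workflow, same 1,000 Veterans.** Control Arm Content puts the control session at about 60 minutes, similar to the intervention. Design gives 30–60 minutes for both. The Indirect cost paragraph drops the control session from the cost estimate because it would not occur in usual care. The workflow sentence subtracts control-arm time and states no such exclusion.

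| T_int (min) | T_ctl subtracted (min) | Planned hours, 1,000 Veterans | Hours for 350 eligible, no control session |
|---|---|---|---|
| 60 | 0 | 1,000 | 350 |
| 60 | 60 | 0 | 350 |
| 30 | 60 | −500 | 175 |

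The planned figure falls below the eligible-population figure whenever (T_int − T_ctl)/T_int is less than d × s. At d × s = 0.35 and T_int = 60, that means a control time above 60 × (1 − 0.35) = 39 minutes.

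**Screening.** Finding one screen-positive drop user takes 1/s screens: 1/0.9 = 1.1 to 1/0.3 = 3.3 over the assumed range. At d = 0.7, 700 of the 1,000 would be screened. At an assumed 5–10 minutes each, that adds 700 × 5/60 = 58 to 700 × 10/60 = 117 hours, which offsets part of the reduction in headcount.

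**The case against.** The strongest reply is that a health system might offer the programme to everyone, and that the screener is a recruitment device rather than a rollout rule. Part of this stands. No section says that a VA programme would be limited to screen-positive Veterans, so that restriction is a scenario. Restriction to drop users is not optional, however, and offering the programme to all drop users would still borrow a utilisation difference measured only in those who screened positive. It can likewise be argued that recruitment calls are study-driven and properly left out. That holds for the trial's own calls, but a targeted programme would need some form of screening.

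A second reply is that the size of the error is unknown. That is fair: both shares are assumed, and the base count cannot be checked. The two sections also describe it differently, one as US prevalence and the other as rates among Veterans.

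A reader might infer that both the dollar and the FTE figures are overstated, and by a common factor. The documents do not support this. The budget figure is a net difference of unknown sign, and the workflow figure can be near zero or negative if the control session is subtracted. Nor is there a common factor once per-patient differences vary between groups or screening is added; 1/(d × s) is a ratio of headcounts only.

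**Conclusion.** The mismatch is real and nothing elsewhere in the documents corrects it. The multiplier is too large for the population studied, by 1/(d × s) before any open-angle restriction. This is about 1.2 to 6.7 under the assumed shares (50–90% on drops, 30–90% screening positive). With the per-patient difference held fixed, the absolute size of each total is inflated by that factor. The direction of error in the net budget and workflow figures is not determined. Confidence is high for the mismatch and low for its size. The consequence is confined to the planning extrapolation in Aim 3, but that extrapolation exists to be used by administrators, so it is worth correcting before the analysis.

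**What to change.** 1. Base case: count VA patients with open-angle glaucoma who are prescribed drops directly from the Corporate Data Warehouse, and multiply by the screen-positive share from the trial's screener survey. Give a range for that share, and state that those screened were selected: they had an upcoming appointment, did not opt out, were reached and were interested. A direct count avoids applying a share from VA records to a prevalence-based total.
2. Add screening time and cost for every Veteran screened in this targeted scenario.
3. Show all drop users as an alternative scenario, with the caveat that the utilisation difference was measured only in screen-positive Veterans. Show the all-glaucoma count only as an upper bound on headcount.
4. For workflow, leave the study-only control session out of control-arm time, in line with the cost rule in the Indirect cost paragraph.
5. Align the wording of the Aim 3 text under Outcomes with the Budget and Workflow Impact paragraph.

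The cost is small. No new participant data are needed: screener responses are already captured, and drop prescription is already a data-pull criterion. The trial's own pull covers patients with appointments at one medical center, so a system-wide count needs a broader query, and the documents do not say whether current approvals cover it. The apparent reach of the programme will be smaller, and the result becomes a set of scenarios rather than one number.
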